- Describe the causes of non-performance of the confirmatory test and identification of predictors of non-performance or postponement of the diagnostic test within a maximum period of 90 days from the initial recommendation.

Study design

Overview

Study, prospective, open, randomized, controlled.

Justification of the main elements of the protocol

The FINDRISC screening questionnaire has been previously studied and validated, can be applied quickly, economically and its low complexity makes them widely available (5,10). Similarly, previous studies have shown that periodontal disease is related to the appearance of alterations in the glycemic profile so that up to 30% of adults over 30 years of age who attend general dentistry consultations are identified as a population at risk (3).

Despite the drawbacks to its mass application, OGTT remains included within the current CPGs and continues to be a reference test for the diagnosis of patients with DM2 (3).

Measurement of A1c may be more convenient than OGTT, particularly if performed at the point of care (POC-A1c). Additionally, the characteristics for its implementation and its technical profile are clearly established. However, its impact on the screening algorithm under real conditions of use is unknown and its profile for inclusion within a mass screening system has not yet been established.

Setting the primary endpoint

While it is possible to perform screening using any of the validated questionnaires, in real conditions of their implementation a second visit of the patient is required to perform a confirmatory test (GTT) and the loss to follow-up is required a major challenge for health systems. It is proposed that the implementation of POC-A1c can contribute to improving the follow-up rate in the context of population screening and facilitate the successful implementation of large-scale screening campaigns.

Therefore, the primary outcome is the probability of going to OGTT according to the strategy implemented.

Choice of comparator

Currently, the screening guidelines contemplate the completion of the FINDRISC questionnaire followed by a confirmatory test carried out in the centralized laboratory. Because of this, the recommended practice is established as a comparator.

Type of design

Prospective, open label, randomized, controlled study in adults with no known diagnosis of diabetes.

Study procedures

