After 30 days from the application of the screening, a call will be made to the randomized subjects to check if they performed the indicated diagnostic test and the result of the OGTT, if the examination has been carried out, must be sent to the center (either by scanning, photographing, or bringing it to the research center). Otherwise, the causes of non-realization of the same will be investigated and a new call will be made after 90 days. In patients who, if they attended the performance of the OGTT and obtained a presumptive result of diabetes, a closing call will be made 30 days after the test was performed to confirm if they began control of their disease. For this, you will be instructed to attend a consultation by general medicine according to what is contemplated by your entity administering benefit plans, ending the follow-up.

Study population

Adult patients with no known diagnosis of diabetes attending a health care facility.

Inclusion criteria

- Adult, aged 18 years or older and under or equal to 75 years old
- Understand, accept, and sign informed consent
- FINDRISC greater than or equal to 12

Exclusion criteria

- Previous diagnosis of type 1 or type 2 diabetes mellitus
- Pregnancy or lactation at the time of inclusion in the study (referred by the subject)
- History of cancer in the subject (must be in remission for 5 years)
- Known history of familial hyperlipidemia
- Chronic use of systemic corticosteroids (Defined as: a dose greater than 5 mg of oral prednisolone or its equivalent and/or consumption greater than one month thereof).
- Known history of hemophilia or other bleeding disorders
- Known history of stage IV or V chronic kidney disease
- Known history of HIV
- Known history of sickle cell disease
- Known history of 6 phosphate dehydrogenase deficiency
- Known history of blood transfusion in the past 3 months
- Known history of erythropoietin therapy in the past 6 months.

Criteria and procedures for the withdrawal or suspension of subjects

Type and time of data collection corresponding to withdrawn subjects

The subject who decides to participate in the study can choose to withdraw at any time, since no therapeutic interventions are being applied, only guidance will be offered to the subject regarding their risk condition as has been established until that moment of the study and the moment in that its follow-up is terminated.

Whether to replace subjects and how

Withdrawn subjects will not be replaced.

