The random allocation sequence will be automatically generated through the platform intended for this purpose. A member of the research team will record the group to which the participant was assigned on the data logging platform.

Instructions to the patient

In Pre-Screening activities, a member of the research team must give the participant a flyer with educational information about healthy lifestyles, regardless of the participant's score. In addition to all participants who enter the study, they will be given an order for the realization of the PWG with the relevant indications for the taking of the sample and the flyer mentioned above.

In this documentation must be the sequence number that was assigned to the patient, as well as their identification number so that when they go to the sampling site (CAIMED allied laboratory/Laboratory of their preference) they are identified as a participant in the study. This will make it possible to monitor which participants have already completed the GGP. 30 days after applying the screening questionnaire or the completion of the GTT, the follow-up call is made.

The script is as follows:

"Good morning / good afternoon / good evening, Madam/Sir (name of the subject). My name is (Contributor Name) I am (Position) We are calling you on behalf of the diabetes early detection study. As you recall, on the day (date

	
Effectiveness comparison of the hemoglobin measurement glycosylated at the point of care (POC-A1c), vs the standard current based on tolerance test oral to glucose, for the detection early of Diabetes Mellitus guy 2 (DM2) in Colombia. EDDIT-1 STUDY
	
Version: 3.0 Date: February 15, 2022

---	--	---

of inclusion in the study) you participated in the site (inclusion site to the study) in the diabetes study. I would like to know if you had the sugar test indicated by the doctor (corresponding to the day of completion of window 1 for the OGTT).

(Wait for a reply)

If the patient replies that the test was performed, the date and result should be confirmed and ask: "Could you please send us a photo or any proof of the report? Finally, the call should end like this: "Thank you very much Ms./Mr. (name of the subject). Remember to consult your doctor or your EPS to initiate timely management of the disease (in case it is impaired) or monitor the risk at least annually."

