If the answer is I have not taken the test: Could you please tell us why you have not taken the sugar test? Wait for a response, and document it, end the call like this: "Remember that we will call you in 2 months again to confirm if the test was done."

**The answers are recorded by the platform and will be analyzed qualitatively by the researchers.*

Scheduling of study visits (schedule)

Responsible	Prescreening	Visit 1	Phone Call 1 (30 days ± 3 days)	Phone Call 2 (90 days ± 3 days)	Phone Call 3 (30 days after reporting to the center ± 3 days, if applicable)
Doctor Bacteriologist Research Assistant	– Conferences of application of FindRisc as risk screening				
Doctor		Explanation of the study, its procedures and obtaining the consent informed. Review of eligibility criteria.			
Research Assistant		VERIFICATION of FINDRISC, Randomization and data processing on the platform			
Research Assistant		Data processing on the platform to the corresponding group			
Laboratory		Implementation of POC-A1c			

Effectiveness comparison of the hemoglobin measurement glycosylated at the point of care (POC-A1c), vs the standard current based on tolerance test oral to glucose, for the detection early of Diabetes Mellitus guy 2 (DM2) in Colombia. **EDDIT-1 STUDY**

Version: 3.0
Date: February 15, 2022

CRS			Follow-up call 30 days after the PGT request.	Follow-up call - 30-90 days after admission to the study in patients not attending OGTT.	Verification call 30 days from the report of the result of the requested test. To those who present an impaired OGMP and have requested a control doctor.

Bias Control

- **Bias derived from the randomization process:** it is carried out through the Office - Excel platform by means of algorithms for the generation of random numbers and their assignment to the specific group, by means of a simple impaired randomization; in order to maintain the masking of the assignment, a number (1-2) will be assigned to classify the intervention and its comparator, keeping this hidden from most researchers.
- **Bias due to deviations from planned interventions:** from study design, with simple randomization, the subject who has received a group assignment cannot move on to the other.
- **Bias due to the lack of outcome data:** The number of stratified lost data of intervened versus non-intervened will be evaluated, if it exceeds 5% analysis and data imputation will be made.

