- **Bias in outcome measurement:** the outcome of the OGTT sampling is sufficiently robust not to be affected by the research team, the participant itself or external factors.
- **Bias in the selection of the reported result:** at this point it is mentioned how the creation of surrogate outcomes not proposed in the protocol will be avoided and how consistency will be maintained in terms of the applicability of statistical terms, that is, only what is proposed in the data analysis will be carried out.

Statistical analysis plan

Description of statistical methods

For the primary objectives, the proportions of patients who attended the performance of the GTT in each of the groups will be obtained and the statistical significance test will be applied for superiority in the follow-up ratio of the intervention group (A) over the control group (B). Additionally, descriptive statistics will be obtained regarding the dynamics of application of the confirmatory test (i.e., latency time).

The variables will be checked for normality using the Kolmogorov-Smirnoff test. For quantitative variables, data shall be expressed as mean and standard deviation, or median and interquartile range 25%-75%, as the case may be.

For qualitative variables, proportions (%) will be determined. The continuous data between both groups will be analyzed with the T test if the distribution of the variables is normal or with the Mann-Whitney test if they are not. The analysis of the categorical data between two groups will be carried out with the chi-Square or Fisher test as appropriate.

An analysis will be carried out on the conditional probability of reaching a OGTT test: $P(\text{perform OGTT} | \text{FINDRISC} \geq 12)$

$P(\text{perform OGTT} | \text{POC-A1c} \geq 5.7\% \text{ and FINDRISC} \geq 12)$

An analysis will be performed to identify risk factors for not performing the PGT, the dependent variable will be dichotomous. The main independent variable will be dichotomous corresponding to the control and intervention group. The control variables will be: age,

	
Effectiveness comparison of the hemoglobin measurement glycosylated at the point of care (POC-A1c), vs the standard current based on tolerance test oral to glucose, for the detection early of Diabetes Mellitus guy 2 (DM2) in Colombia. EDDIT-1 STUDY
	
Version: 3.0 Date: February 15, 2022

---	--	---

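### Attendance at the OGTT is recorded through staff calls and participant-sent proof in an open-label trial, so it is not immune to arm-related recording error, as the Bias Control section states

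*Combined protocol and SAP*

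**What the plan says.** The section on setting the primary endpoint defines the outcome as attendance, not the glucose value: "the primary outcome is the probability of going to OGTT according to the strategy implemented". The design is "Prospective, open label, randomized, controlled study in adults with no known diagnosis of diabetes".

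Under Bias Control, the item on outcome measurement says that "the outcome of the OGTT sampling is sufficiently robust not to be affected by the research team, the participant itself or external factors".

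The procedures for recording attendance are spread over several sections:

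- **Place of test** (Study procedures): the partner laboratory or any laboratory the participant prefers.
- **Calls** (Instructions to the patient; visit schedule): staff telephone at 30 days, and again at 90 days those who have not attended. The script says "I would like to know if you had the sugar test indicated by the doctor".
- **Proof**: Study procedures says the result "must be sent to the center (either by scanning, photographing, or bringing it to the research center"). After a yes, the script confirms date and result and asks "Could you please send us a photo or any proof of the report".
- **Laboratory identification** (Instructions to the patient): the order carries the sequence number and an ID, for use at either kind of laboratory. "This will make it possible to monitor which participants have already completed the GGP".
- **Masking** (Bias Control, randomization item): the group is coded 1 or 2, "keeping this hidden from most researchers".
- **Missing outcomes**: Bias Control compares losses by arm and imputes above 5%. The section on selection of subjects keeps only individuals with complete data.

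**The concern.** Whether someone had an OGTT is an objective fact. Whether the trial records it depends on a caller reaching the participant, on what the participant says, and on whether a report arrives. These are the research team and the participant, whom the Bias Control statement says cannot affect the outcome.

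Participants know whether they had a POC-A1c, and group A has had an extra test and more contact with staff. Willingness to answer the call or send proof may therefore differ by arm. The plan does not say how to count a yes without proof, a test done but never reported, or a participant who cannot be reached. Under-recording that is equal in the two arms does not inflate the type I error. Unequal recording biases the only primary comparison, in either direction.

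**Working it through.** **Inputs from the plan.** Attendance 60% (A) v 50% (B), power 80%, 392 per arm before adjustment, 510:392 after it (Sample size); significance level 0.05 (Level of significance). Sidedness is not stated.

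**Reproducing the sample size.** Pooled two-proportion formula, two-sided 0.05:

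n = [1.96·√(2·0.55·0.45) + 0.842·√(0.5·0.5 + 0.6·0.4)]² / 0.10² = 388 per arm.

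This is close to the plan's 392 (taking p = 0.5 throughout gives 393). One-sided versions give 303 to 325 and do not fit, so two-sided 0.05 is used below. Then 392 × 1.3 = 509.6, or 510, and 510 + 392 = 902. Power for 60% v 50% is 80.5% at 392:392 and 85.1% at 510:392.

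**Assumed inputs.** The documents give no rates for return of proof. Let s be the share of true attenders whose attendance is recorded, with nobody falsely recorded. Recorded attendance is then true attendance × s in each arm.

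**Rejection probability.** With recorded rates pA and pB, d = pA − pB and pooled rate p = (510·pA + 392·pB)/902:

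SE0 = √[p(1 − p)(1/510 + 1/392)]

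SE1 = √[pA(1 − pA)/510 + pB(1 − pB)/392]

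P(reject) = 1 − Φ[(1.96·SE0 − d)/SE1] + Φ[(−1.96·SE0 − d)/SE1]

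**No true effect (50% in both arms):**

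| s in A | s in B | pA | pB | False difference | Type I error |
|---|---|---|---|---|---|
| 95% | 95% | 0.475 | 0.475 | 0 | 5.0% |
| 95% | 93% | 0.475 | 0.465 | 1.0 point | 6.0% |
| 95% | 90% | 0.475 | 0.450 | 2.5 points | 11.6% |
| 95% | 85% | 0.475 | 0.425 | 5.0 points | 32.1% |

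Last row in full: p = 0.4533, SE0 = 0.03344, SE1 = 0.03335, (1.96 × 0.03344 − 0.05)/0.03335 = 0.466, and 1 − Φ(0.466) = 0.321. Nearly all of it is false superiority of A. Simulation with 200,000 runs gave 32.2% for this row and 11.6% for the row above it.

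**True effect as designed (60% v 50%), gap in the other direction.** Recording 85% of A and 95% of B gives pA = 0.6 × 0.85 = 0.510 and pB = 0.5 × 0.95 = 0.475. The 10-point difference shrinks to 3.5 points, and power falls from 85.1% to about 18%.

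**Scale.** With 50% recorded in B, an observed difference of about 6.7 points (289/510 = 56.7%) is already significant.

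**The case against.** The strongest reply is that the plan does not rest on a bare yes. The result has to reach the center, the caller confirms date and result, and Annex 4 records an OGTT date and a value in mg/dl with no self-reported attendance item. A false claim would need an invented date and result. This stands: false claims are the less likely route, and differential return of proof is the likelier one.

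The plan also provides for participants to be identified at both kinds of laboratory. A reader might infer that outside the partner laboratory the participant is the only possible source; the text on the order number does not support that. What is missing is any description of how a laboratory's record reaches the center.

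A reader might also infer that the callers know the arm. The documents do not say so. The group code is hidden from most of the team, the schedule lists the calls under a different role from the one that randomizes, and the script mentions neither arm nor POC-A1c. But callers are not said to be among those masked, and participants cannot be.

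Comparing losses by arm, with imputation above 5%, helps only where an unreported test is classed as missing and not as non-attendance, which the plan leaves open.

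Finally, the rates are assumed, and a small gap does little: 95% v 93% moves the type I error only to 6%.

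**Conclusion.** The robustness statement conflicts with the plan's own procedures and should not stand. The documents show that the primary outcome is exposed to recording error that may differ by arm. They do not show that such error will occur, how large it would be, or which arm it would favor. It would go too far to conclude that the trial is biased toward the intervention, since the same mechanism can hide a real benefit.

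Under assumed recording rates, a gap of 2 to 10 percentage points between arms takes the type I error from the nominal 5% to between about 6% and 32%. A 10-point gap the other way cuts power from 85% to about 18%. These figures assume a two-sided pooled test at 510:392, everyone counted, and no false claims. This is a cheap improvement to outcome ascertainment, not a fatal flaw.

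**What to change.** 1. Withdraw the robustness statement and describe how attendance is established.
2. Use the existing order number and ID to check partner-laboratory records for every randomized participant in both arms at the 90-day cut-off, whether or not the call is answered. Where a participant names another laboratory, ask it to confirm where possible.
3. Hide the arm from the callers and from whoever classifies attendance, through the platform view.
4. Prespecify how an unproven yes is counted. Report the primary comparison under both definitions: attendance verified by laboratory record or report, and verified plus self-reported. Give proof-return rates by arm.

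A proof-only definition would not be enough. If no one used the partner laboratory, 95% v 85% proof return would leave the type I error at 32%. If half of attenders in each arm used it and all of those were matched, recording would be 0.5 × 100% + 0.5 × 95% = 97.5% v 0.5 × 100% + 0.5 × 85% = 92.5%, and the error about 11.5%. This is why both definitions are needed.

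**Cost.** Protocol and SAP wording, a platform setting and some record matching. Verified attendance may be slightly lower. Some bias remains for laboratories of choice, where proof still depends on the participant.

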Objectives	In patients at risk identified by FINDRISC (i.e., score greater than or equal to 12), determine the difference in the number of patients who attend a confirmatory test (GTT) after the isolated application of the screening questionnaire versus the completion of the supplemented questionnaire by POC-A1c.
Study design	Prospective, open label, randomized, controlled study.
Population	Adult patients with no known diagnosis of diabetes
Inclusion criteria	
 • Adult, aged over or equal to 18 years and less than or equal to 75 years. • Understand, accept, and sign informed consent • FINDRISC greater than or equal to 12
Exclusion criteria	
 • Previous diagnosis of type 1 or type 2 diabetes mellitus • Pregnancy or lactation at the time of inclusion in the study (referred by the subject). • History of cancer in the subject (must be in remission for 5 years) • Known history of familial hyperlipidemia. • Chronic use of systemic corticosteroids (Defined as: a dose greater than 5 mg of oral prednisolone or its equivalent and / or consumption greater than one month thereof). • Known history of hemophilia or other bleeding disorders • Known history of stage IV or V chronic kidney disease • Known history of HIV (on antiretroviral therapy) • History of sickle cell disease • Known history of glucose 6 phosphate dehydrogenase deficiency • Known history of blood transfusion in the past 3 months • Known history of erythropoietin therapy in the past 6 months.
Duration of the study	Each subject will participate in the study approximately 4 months, in addition, each patient will be given a follow-up call 30 days and 90 days from the date of inclusion in the study.

	
Comparative effectiveness of point-of-care glycosylated hemoglobin measurement (POC-A1c), vs. the current standard based on oral glucose tolerance test, for the early detection of Type 2 Diabetes Mellitus (T2DM) in Colombia. EDDIT-1 STUDY
	
Version: 3.0 Date: February 15, 2022

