
Procedures
	
The doctor explains what the study consists of and obtains informed consent. If the patient accepts, the FINDRISC will be verified, the inclusion and exclusion criteria are verified and the relevant data from their medical history will be recorded.
 
Subsequently, the subjects will be included in the study and randomized into two groups. In the participants of group A (intervention) they will be offered information on healthy lifestyles according to their result in the FINDRISC questionnaire and then a measurement of POC-A1c. In the participants of group B (control) they will be offered the same information on healthy lifestyles according to their FINDRISC result.
 
In addition, all randomized participants will be invited to perform a GPOT in the allied work of CAIMED or in the laboratory of their choice with the necessary preparation recommendations for the realization of the same. For this purpose, they will be given an order that includes the date of screening, a tracking number and time window in which they must go (i.e., 30 days and with a second attempt-maximum window at 90 days).
 
After 30 days from the delivery of the order for the PGTO, a call will be made to the randomized subjects to check if the exam was taken and its result requested in case it has done so, if the examination, you must send it to the center. Otherwise, the causes of not having made the previously recommended GTT will be investigated, and a new call will be made after 90 days. In patients who, if they attended the performance of the OGTT and obtained a presumptive result of diabetes (defined as an impaired oral glucose tolerance test and/or impaired POCA1C test according to the ADA guidelines), a closing call will be made 30 days after the test was done to confirm if they started to control their disease. For this, it will be instructed to attend consultation by general medicine according to what is contemplated by its entity administering benefit plans, ending the follow-up.
	

Analysis plan
	
For the primary objectives, the proportion of patients who attended the performance of the PGTT in each of the groups will be obtained and the statistical significance test for superiority in the follow-up ratio of the intervention group (A) over the control group (B) will be applied. Additionally, descriptive statistics will be obtained regarding the dynamics of application of the confirmatory test (i.e., latency time).
	

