One disadvantage that has been pointed out about point-of-care testing is that its unit cost is higher compared to tests performed in a processing center. However, this agreement only considers the direct cost of the test and does not know the impact that the immediate diagnosis generates on other costs, such as the need for successive consultations and the avoidable morbidity that occurs because of the loss of follow-up to the patient.

Additionally, to make point-of-care testing affordable, it is necessary to design and implement an operating model that is very different from the traditional central laboratory model, for this, it is necessary to contemplate the screening of populations that go to other health services in those that have been identified as having an increased risk. For example, it has been documented that periodontal disease is associated with diabetes so that in adults over 30 years of age who attend general dentistry consultations, up to 30% of patients with alterations of the glycemic profile can be found (9).

In this frame of reference, it is proposed that to significantly increase the early detection of patients with DM2 it is necessary to explore alternatives for active search for patients with prediabetes or undiagnosed diabetes. These alternatives may include the completion of a screening questionnaire and a confirmatory test at the point of care, however, to achieve a higher rate of early detection it is necessary to find a balance between adequate sensitivity and specificity with less loss of follow-up.

Primary objectives

- In patients at risk identified by FINDRISC (i.e., score greater than or equal to 12), determine the difference in the number of patients attending a confirmatory test (GTT) after the isolated application of the screening questionnaire versus the completion of the questionnaire supplemented by POC-A1c.

Secondary objectives

- To determine the probability of attending a confirmatory test (GTT) for DM2, in the population at risk identified by FINDRISC.
- To determine the probability of attending a confirmatory test (GTT) for DM2, in the risk population identified by FINDRISC in whom POC-A1c was applied.
- Determine the performance in terms of time and adherence of the application of POC-A1c against the current recommendations in the GPC (ADA).

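### The time objective is comparative, but the only planned time analysis is latency among those who attend; attendance over time in all randomised participants is not planned (minor).

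*Combined protocol and SAP*

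**What the plan says.** The third item under Secondary objectives is comparative: "Determine the performance in terms of time and adherence of the application of POC-A1c against the current recommendations in the GPC (ADA"). It does not say what time is measured from or to. The next item asks for predictors of not doing the test, or of postponing it, "within a maximum period of 90 days from the initial recommendation".

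On method, the synopsis (Analysis plan) and Description of statistical methods name time once each, in the same terms: "descriptive statistics will be obtained regarding the dynamics of application of the confirmatory test (i.e., latency time"). The primary analysis compares proportions attending. The regression has a yes/no outcome, the OGTT not done. The documents contain no cumulative attendance curve, day-30 comparison or time-to-event analysis.

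Three other places bear on this:

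- Bias Control states that "only what is proposed in the data analysis will be carried out", and sets an imputation rule when lost data exceed 5%.
- Selection of subjects to be included in the analyses limits the final analysis to individuals with complete data.
- Annex 4 records the OGTT date. It lists neither an order date nor a last-contact date.

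**The concern.** Latency needs an OGTT date, so it exists only for attenders. Attending is the primary outcome and is what POC-A1c is meant to change. The two groups of attenders are therefore formed after randomisation, by a process that differs between the arms. A side-by-side latency figure mixes two things: how soon people come, and which people come at all.

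If POC-A1c brings in extra people who would otherwise have stayed away, and they come late, average latency in A rises although no one was slowed. A reader could then conclude that the strategy delays testing when attendance in A is at least as high at every time point. At stake is how one secondary objective is reported. The commitment to run only planned analyses makes it better to settle this now than after the data are in.

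**Working it through.** **Inputs.** Attendance of 60% (A) and 50% (B), 392 per arm before adjustment, and 510 + 392 = 902 after it, are from Sample size. The 90-day maximum window is from Study procedures. The documents give no timing of attendance, so every timing figure below is an assumption.

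**1. The plan's own figure.** 2 × 0.25 × (1.96 + 0.84)² / 0.10² = 392 per arm. Then 392 × 1.30 = 509.6, rounded to 510, and 510 + 392 = 902. The stated sizes reproduce.

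**2. Who has a latency.** A: 510 × 0.60 = 306. B: 392 × 0.50 = 196. Without one: 204 + 196 = 400 of 902 (44.3%).

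**3. What latency can show.** Assume B attends 40% in days 1–30 and 10% in days 31–90, evenly within each period (mean days 15.5 and 60.5). A totals 60%, and the timing of its extra 10 points varies.

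- Mean latency = (early × 15.5 + late × 60.5) / (early + late). For B: (40 × 15.5 + 10 × 60.5) / 50 = 24.5 days.
- Median = 0.5 + 30 × (half of total attendance / early attendance). For B: 0.5 + 30 × 25/40 = 19.25 days.
- Day-30 half-width = 1.96 × √(pA(1−pA)/510 + pB(1−pB)/392).

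As a fifth case, take a constant attendance rate in each arm, λ = −ln(1−p)/90. The median attender is at −ln(1−p/2)/λ and the mean is 1/λ − 90(1−p)/p.

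| A's extra attenders | Mean A vs B (days) | Median A vs B (days) | Day-30 difference, A − B (points) |
|---|---|---|---|
| all late (40 + 20) | 30.5 vs 24.5 | 23.0 vs 19.25 | 0 ± 6.5 |
| half late (45 + 15) | 26.75 vs 24.5 | 20.5 vs 19.25 | 5 ± 6.5 |
| timed as in B (48 + 12) | 24.5 vs 24.5 | 19.25 vs 19.25 | 8 ± 6.5 |
| all early (50 + 10) | 23.0 vs 24.5 | 18.5 vs 19.25 | 10 ± 6.5 |
| constant rates | 38.2 vs 39.8 | 35.0 vs 37.4 | 5.7 ± 5.5 |

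A's mean latency runs from 6 days longer to about 1.6 days shorter than B's. Its median runs from 3.75 days longer to about 2.3 days shorter. The day-90 difference is 10 points (95% CI 3.5 to 16.5) in every row, assuming no loss to follow-up. The rows were chosen so that A's cumulative attendance is never behind; that is not a result.

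**4. Would a log-rank test add much?** In 3,000 simulated trials for each of the first four rows, the log-rank statistic correlated about 0.97 with the primary two-proportion statistic. When attenders' timing is identical in the two arms, it still exceeds z = 1.96 in favour of A in a little over 80% of trials. It mainly re-measures how many attend, not how fast attenders come.

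**The case against.** **Time is not defined.** The objective could mean the time the strategy takes to yield a glycaemic result, and then neither latency nor an OGTT curve answers it. This stands. Reading it as time to the OGTT is an assumption, supported by the latency description in the statistical methods and by the objective on postponement.

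**The 400 without a latency are not lost data.** A reader might infer from the 44% that the trial loses nearly half its data. It does not: time to a test is undefined for someone who never takes it, and the primary proportion already counts non-attenders.

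**The plan calls latency descriptive and announces no test of it.** Also correct. A reader might infer that the general t-test or Mann-Whitney rule for continuous data will be applied to latency, but that rule does not name latency and this point does not assume it. What remains is that a comparative objective has only a description that cannot support a comparison.

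**The reversal depends on assumed timing.** It does. Of the five rows, two make A look slower, one shows no difference and two make A look quicker. The documents do not support saying that A will look slower.

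**A curve in all randomised participants has its own problems.** Censoring at last contact assumes that unreached people attend like the rest. If 20% of non-attenders were never reached and were censored at day 0, the curve would read 60/92 = 65% and 50/90 = 56% instead of 60% and 50%, and would compete with the primary result. The complete-data rule could also be read as removing non-attenders. Both objections stand and shape the fix.

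**The call clocks.** A reader might infer a conflict from the different starting points, such as "each patient will be given a follow-up call 30 days and 90 days from the date of inclusion in the study", "After 30 days from the delivery of the order for the PGTO" and "After 30 days from the application of the screening". Most appear to coincide at Visit 1. This is a side point of wording and the conclusion does not rest on it.

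**Conclusion.** The point holds as a minor one. If time in the secondary objective means time to the OGTT, the plan has no analysis that can answer the comparison. Descriptive latency covers only attenders and, read by arm, conditions on the primary outcome. The counts of 306 and 196 follow from the plan's design rates and are expected, not observed. The size and direction of any misleading latency difference rest wholly on assumed timing, and apparent slowness of A requires its extra attenders to come disproportionately late.

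Nothing here touches the primary endpoint, its test or the sample size. A reader might infer a flaw in the main comparison, but the documents do not support that.

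**What to change.** In Description of statistical methods:

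1. State that time in the secondary objective means time from the OGTT order at Visit 1 to the OGTT date. If the sponsor means something else, say so and name the analysis for it.
2. Report cumulative attendance by arm in all randomised participants, with the between-arm difference and 95% CI at day 30.
3. Take day 90 from the primary analysis and do not estimate it a second time.
4. State that a participant without an OGTT date because no test was taken has complete data for this analysis, so that the complete-data rule does not drop non-attenders.
5. Treat unreached or withdrawn participants by the same rule as in the primary analysis, including the over-5% rule in Bias Control. Use censoring at last contact only as a sensitivity analysis.
6. Keep latency as a description, labelled as conditional on attending, with no between-arm test.
7. A log-rank test is optional. If used, describe it as comparing attendance over time and note that it largely repeats the primary.

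The cost is a paragraph of text, one more secondary analysis, and an order date and a last-contact date in Annex 4. The OGTT date is already collected, and the first call already asks about test status at 30 days.
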